Study To Evaluate The Efficacy Of Tofacitinib In Patients With SJS/TEN

ClinicalTrials.gov ID NCT06474078

Sponsor Chang Gung Memorial Hospital

Information provided by [name], Chang Gung Memorial Hospital (Responsible Party)

Study Overview

Brief Summary

The goal of this study is to evaluate the effect of tofacitinib in patients with Stevens-Johnson Syndrome (SJS) and Toxic Epidermal Necrolysis (TEN). The primary outcome of the study is the time to complete re-epithelialization. The secondary outcomes are to determine mortality, length of hospitalization, adverse events, the time to beginning of epithelialization, the time to halting of progression of SJS/TEN, ocular complications, and infections.

Detailed Description

Stevens-Johnson syndrome (SJS) and toxic epidermal necrolysis (TEN) belong to life-threatening severe cutaneous adverse drug reactions. SJS/TEN is classified by the extent of the detachment over the total body-surface area: SJS (<10%), SJS-TEN overlap (10%-30%), and TEN (>30%). TEN has the highest mortality (30-35%); SJS and transitional forms correspond to the same syndrome, but with less extensive skin detachment and a lower mortality (5-15%). Currently, there is still no conclusive effective immunomodulator treatment for SJS/TEN. And, there is still a clinical unmet need for the treatment of SJS/TEN.

According to our past research reports, interleukin-15 (IL-15) plays an important role in SJS/TEN, which is related to disease severity and mortality. Janus kinase (JAK) inhibitors can inhibit the downstream JAK to inhibit the production and transmission of inflammatory cytokines, as a treatment for severe skin drug hypersensitivity reactions. Tofacitinib, a JAK1/3 inhibitor, is an intervention known to effectively treat several inflammatory diseases including rheumatoid arthritis, psoriatic arthritis, and ulcerative colitis. Notably, a recent study identified a potential therapeutic target with JAK-STAT pathway in a patient with recalcitrant and refractory drug rash with eosinophilia and systemic symptoms (DRESS). Based the current evidence, a targeting therapy to IL-15 by tofacitinib treatment are suggesting likely to be effective in treating SJS/TEN.

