This is an "open label" study, all patients enrolled in the study will receive the active medication; meaning that there will not be a placebo or control group. The aims of this project are (1) to investigate the effect of tofacitinib treatment for SJS/TEN patients, including healing time, mortality rate, adverse events, beginning of re-epithelialization time, internal organ recovery time, and ocular complications, and (2) to investigate the molecular mechanism of SJS/TEN after tofacitinib treatment through collection of timed samples to include DNA, RNA, PBMCs, blister cells and supernatant and skin tissue.

The primary outcome of the study is the time to complete re-epithelialization as defined by complete absence of erosion on the skin. The secondary outcomes are to determine the time to beginning of epithelialization (defined as the time to start re-epithelialization of the erosions on the skin and mucosa), the time to halting of progression of SJS/TEN (considered significant progression if there are any new blistering lesions or any new detached or detachable skin), mortality, length of hospitalization, ocular complications, infections, and adverse events. The investigators also determine the molecular and cellular mechanisms of SJS/TEN through collection of timed samples to include DNA, RNA, PBMCs, blister cells and supernatant and skin tissue.

Official Title

An Open-Label Pilot Study to Evaluate the Safety, Tolerability, and Efficacy of Tofacitinib in Patients With Stevens-Johnson Syndrome (SJS) and Toxic Epidermal Necrolysis (TEN)

Intervention / Treatment

Drug: Tofacitinib

Other Study ID Numbers

IRB No. 202102411A3

Contacts and Locations

This section provides the contact details for those conducting the study, and information on where this study is being conducted.

Study Contact (Project Leader)

Name: [name]

[contact] [name]

Email: [contact]

Study Contact Backup (Co-Investigator)

Name: [name]
[contact] [name]
Email: [contact]

Name: [name]
[contact] [name]
Email: [contact]

Participation Criteria

Researchers look for people who fit a certain description, called eligibility criteria. Some examples of these criteria are a person's general health condition or prior treatments.

Eligibility Criteria

Description

Inclusion Criteria:

1. Willing to sign informed consent form
2. Subject has been diagnosed with Stevens-Johnson syndrome or toxic epidermal necrolysis by at least two dermatologists.

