3. Male or female aged over 20 years old and under 90 years old.

Exclusion Criteria:

1. Subject or legally authorized representative is not willing to provide informed consent.
2. Women who are pregnant or breastfeeding
3. Subject has an active, untreated, or serious infectious disease that is ineffective in treatment, such as sepsis.
4. Subject suffers from severe life-threatening cardiac arrhythmia, such as ventricular tachycardia, have had myocardial infarction (myocardial infarction), severe hypertension that has not responded to treatment within the past week, or other cardiologist diagnosed severe cardiovascular disease
5. Subject has active viral hepatitis
6. Subject has active tuberculosis
7. Subject received live vaccination during the illness

Study Protocol

This section provides details of the study plan, including how the study is designed and what the study is measuring.

How is the study designed?

Design Details

Primary Purpose : Treatment

Allocation : N/A

Interventional Model : Single Group Assignment

Masking : None (Open Label)

Arms and Interventions

Participant Group/Arm 	Intervention/Treatment 

Experimental: Tofacitinib treatment
 
1. Meet the conditions of inclusion and exclusion, seek the consent of the patient2. Fill out the case report form3. Blood test and physiological assessment, and do serum granulysin concentration and peripheral blood mononuclear spherical granulysin expression analysis4. Tofacitinib administration: The experimental group received tofacitinib 5mg-10mg, twice daily, for the first week; and maintained tofacitinib 5mg-10mg, daily, for the second week.	
Drug: Tofacitinib
 
• Dosage/Frequency: 5mg - 10mg, oral, twice daily• Other Names:
▫ XELJANZ

What is the study measuring?

Primary Outcome Measures

Outcome Measure	Measure Description	Time Frame
Time to complete re-epithelialization of SJS/TEN	Definition of complete re-epithelialization as the absence of erosions on the skin.	up to 4 weeks

Secondary Outcome Measures

Outcome Measure	Measure Description	Time Frame
Mortality	Number of participants with mortality at 30 days, 3 months and 1 year	up to 1 year
Length of hospitalization	Duration of hospital stay	up to 3 months
Adverse events	Adverse events related to the treatment with tofacitinib	up to 3 months

Study endpoint

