The endpoint of this clinical trial was defined as the absence of serious or treatment-related adverse events within three weeks after the final tofacitinib dose. Most SJS/TEN patients were monitored for 3–4 weeks post-treatment, with the total observation period spanning 1–2 months. Patients without AEs during this window were considered to have completed the trial and met the safety endpoint.

Study duration

Start Date from 2022-08-01 to 2025-07-31

Statistical Analysis Plan

For evaluating the time taken to heal skin erosion, the Kaplan-Meier product-limit estimates method was performed.

Collaborators and Investigators

This is where you will find people and organizations involved with this study.

Sponsor

Chang Gung Memorial Hospital

Investigators

- Principal Investigator: [name], Chang Gung Memorial Hospital

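### The safety endpoint merges serious events of any cause with drug-related events in a lethal disease with no control group, so its rate cannot be read as the safety of tofacitinib

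*Combined protocol and SAP*

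**What the plan says.** The *Study endpoint* section gives two rules.

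- The definition is the "absence of serious or treatment-related adverse events within three weeks after the final tofacitinib dose". Relatedness is one of two alternatives here, so it does not limit the serious events.
- The working rule closes the section: "Patients without AEs during this window were considered to have completed the trial and met the safety endpoint". It mentions neither seriousness nor causality.

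Neither rule defines a serious adverse event, and neither exempts death or complications from SJS/TEN.

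Elsewhere in the document:

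- The *Detailed Description* gives mortality of 30–35% for TEN and 5–15% for SJS and transitional forms, with no time horizon. It describes the study as open label, "meaning that there will not be a placebo or control group".
- *Arms and Interventions* describes about two weeks of dosing before the three-week window opens.
- *Secondary Outcome Measures* lists mortality ("Number of participants with mortality at 30 days, 3 months and 1 year") and, separately, adverse events attributed to tofacitinib, followed for up to 3 months.
- The *Statistical Analysis Plan* covers healing time only. It gives the safety endpoint no analysis, denominator, reference rate or breakdown by severity.

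**The concern.** Safety and tolerability stand first in the official title, and this is the only measure that the document calls a safety endpoint. As written, one pass/fail label takes in deaths from the disease, serious complications of the disease, and mild reactions to the drug. With no control group there is no background rate to set against the result.

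A low share could be read as toxicity when it reflects how ill the patients were. A high share could be read as safety when few TEN patients were enrolled. The two rules also score some patients differently, so the count depends on which sentence is applied.

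**Working it through.** **Step 1: compare the rules.** The table takes each sentence literally and assumes that a death from SJS/TEN is a serious adverse event.

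| Patient | Definition | Closing sentence | Adverse-event outcome (related only) |
|---|---|---|---|
| Dies of SJS/TEN in the window | fails | fails | not counted; appears under mortality |
| Non-fatal serious event in the window, unrelated | fails | fails | not counted |
| Non-serious event in the window, related | fails | fails | counted |
| Non-serious event in the window, unrelated | passes | fails | not counted |
| Non-fatal serious related event, resolved during dosing | passes | passes | counted |

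The two sentences disagree on the fourth row. In the fifth, a serious drug reaction passes because the window opens only after the final dose. A death during dosing falls inside the window if the final dose means the last dose taken, and outside it if it means the end of the planned course. The document does not say which.

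**Step 2: pass share for a drug with no effect on harm or mortality.** The plan states no target or expected rate, so there is no figure to reproduce. Inputs are mortality *m* from the *Detailed Description* and an assumed share *w* of deaths falling in the window.

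Upper limit on the pass share = 1 − *m* × *w*

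| Group | *m* | *w* = 1 | *w* = 0.5 |
|---|---|---|---|
| TEN | 0.30–0.35 | 65–70% | 82.5–85% |
| SJS/transitional | 0.05–0.15 | 85–95% | 92.5–97.5% |

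With *w* = 1, going from an all-SJS/transitional sample to an all-TEN sample lowers the share by 15 points (85 − 70) to 30 points (95 − 65). With *w* = 0.5 the drop is 7.5 points (92.5 − 85) to 15 points (97.5 − 82.5). The drug is the same throughout.

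**Step 3: add the other components.** Let *d* be the probability of a drug-related event and *s* that of a non-fatal serious disease event, both in the window. Both are assumptions. Take the events as independent and *w* = 1.

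Pass share = (1 − *m*)(1 − *d*)(1 − *s*)

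- *d* = 10%, *s* = 0: TEN 0.65 × 0.90 to 0.70 × 0.90 = 58.5–63%; SJS/transitional 0.85 × 0.90 to 0.95 × 0.90 = 76.5–85.5%.
- *d* = 0, *s* = 20%: TEN 52–56%; SJS/transitional 68–76%.

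So a drug that harms 10% of patients would score 76.5–85.5% in SJS/transitional forms, above the 65–70% that a harmless drug would score in TEN.

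**Step 4: which component dominates?** Share of failures that are disease deaths = *m* / [1 − (1 − *m*)(1 − *d*)(1 − *s*)].

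| *d* | *s* | TEN | SJS/transitional |
|---|---|---|---|
| 5% | 0 | 90–92% | 51–78% |
| 10% | 0 | 81–84% | 34–64% |
| 30% | 0 | 59–64% | 15–37% |
| 10% | 20% | 60–66% | 16–39% |

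Deaths make up most failures in TEN in these scenarios, but often not in SJS/transitional forms.

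**The case against.** The strongest reply is that the components are already partly separated. Mortality and tofacitinib-related events are outcomes in their own right, and the *Detailed Description* adds infections and ocular complications. The analysis section plans no pass percentage, so a headline safety rate is an inference. This stands as mitigation but does not remove the point. Mortality is counted at 30 days, 3 months and 1 year rather than over this window, the adverse-event outcome keeps related events only, and no outcome reports non-fatal serious events of any cause. The document also does label individual patients as having met the endpoint.

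Second, a disease death may not have been meant as an adverse event, since the term is undefined. That is possible, but then a patient who died of SJS/TEN could be classed as free of adverse events and so as a safety success. Either reading needs repair.

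Third, the closing sentence may be shorthand for the events just defined. If so, the fourth row of the comparison is resolved, but serious events of any cause still count.

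Fourth, the pass shares in step 2 are not firm ceilings. The quoted mortality is disease-wide, the exclusion of uncontrolled infection and severe cardiovascular disease may lower it in this sample, and an effective drug would lower it further. This is accepted: they are illustrations.

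A reader might go further and infer that the endpoint measures the lethality of SJS/TEN and not the safety of tofacitinib. The documents do not support that. The endpoint also fails patients for related events and non-fatal serious events, and which component dominates depends on case mix and event rates that the documents do not give. Nor does it capture every serious event, because of where the window starts.

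**Conclusion.** The concern holds in this form: the share of patients meeting the endpoint blends disease mortality, disease morbidity and drug effects, varies with the mix of SJS and TEN, and has no comparator. It cannot be interpreted as a safety rate for tofacitinib in either direction.

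The possible size is considerable: between severity groups, an inert drug's share could differ by 7.5 to 30 points. That range assumes that disease deaths count as serious adverse events, that enrolled patients have the quoted mortality, and that half to all of the deaths fall in the window. The qualitative conclusion needs none of these figures. It rests on the missing causality limit for serious events, the missing exemption for disease events and the missing control group.

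The separate outcomes keep this from being a complete failure of safety reporting, but the endpoint should be changed.

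**What to change.** Reconcile the two sentences of *Study endpoint* with each other and with the adverse-event row of *Secondary Outcome Measures*, and state whether SJS/TEN death and progression count as adverse events.

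Replace the pass/fail label with three lines for all dosed patients, covering first dose to three weeks after the last dose taken:

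1. death from any cause;
2. non-fatal serious adverse event of any cause;
3. non-serious adverse event, with the treatment-related subset shown.

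Give each line a count, a denominator and an exact 95% interval. Show the investigator's attribution (SJS/TEN, tofacitinib, other) as a descriptor. Report every line by SJS, overlap and TEN. Drop the statement that patients without events "were considered to have completed the trial and met the safety endpoint".

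The cost is mainly one reporting table. Some dosing-period events may have to be retrieved from records, since the contents of the case report form are not shown. The trial loses a single headline safety figure, and intervals will be wide in small severity groups. Without a control group the background rate still cannot be subtracted, but the reader can see what each number contains.

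### One condition, freedom from AEs, decides both trial completion and safety success, so a patient not observed for the full window can count as a success and the completion status of a patient with an AE is undefined

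*Combined protocol and SAP*

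**What the plan says.** The Study endpoint section has three sentences. The first gives the endpoint of the trial as "defined as the absence of serious or treatment-related adverse events within three weeks after the final tofacitinib dose". The second describes follow-up: "Most SJS/TEN patients were monitored for 3–4 weeks post-treatment, with the total observation period spanning 1–2 months". The third classifies patients: "Patients without AEs during this window were considered to have completed the trial and met the safety endpoint".

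No other definition of completion appears. Nothing sets a minimum observation time, and nothing says how a patient who withdraws, dies or is lost within three weeks of the last dose is counted. The Statistical Analysis Plan does not fill the gap. Its one sentence concerns healing: "For evaluating the time taken to heal skin erosion, the Kaplan-Meier product-limit estimates method was performed".

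The Secondary Outcome Measures table treats safety separately. It lists "Adverse events related to the treatment with tofacitinib" with a time frame of up to 3 months, and "Number of participants with mortality at 30 days, 3 months and 1 year" with a time frame of up to 1 year.

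**The concern.** Completing a trial is a statement about follow-up. Meeting a safety endpoint is a statement about outcome. Here both depend on the outcome, and neither depends on how long the patient was seen. AE status can come only from days on which someone was observed. Without an observation requirement, days not seen are in effect scored as days without an event.

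This matters because safety stands first in the official title and the study has no control group. The event-free share would be read as an absolute figure, with no comparator in which the same bias could cancel. Deaths are not a remote case either: the Detailed Description puts mortality in TEN at 30–35%, yet the section does not say how a death inside the window is classed.

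**Working it through.** **Nothing to reproduce.** The documents state no sample size, AE rate, loss rate or target for this endpoint. The check is a reading of the text, followed by illustrations on assumed inputs.

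**1. Is a short window possible on the plan's own figures?** Dosing runs for two weeks (Arms and Interventions) and the endpoint window is three weeks after the last dose, so 14 + 21 = 35 days are needed from the first dose. The lower end of the stated total observation period is one month, 28 to 31 days. If that period starts at the first dose and dosing runs its full length, 28 − 14 = 14 to 31 − 14 = 17 days remain after the last dose, against 21 required. The start of observation is not stated, one month may be a rounded figure, and earlier stopping would lengthen the post-dose period. A shortfall is therefore plausible but not shown.

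**2. Effect of scoring unobserved time as event-free.** Let *m* be the share of patients who leave before the window is observed and *e* the true risk of a qualifying event in the window, the same in those who leave. If all events in those patients are missed and they count as successes:

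- share under the literal rule = (1 − m)(1 − e) + m = 1 − e + m·e, an inflation of m·e;
- share if every short window counts as not met = (1 − m)(1 − e), an error of −m(1 − e).

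| m | e | True share | Literal rule | Short windows counted as not met |
|---|---|---|---|---|
| 10% | 20% | 80% | 82% (+2) | 72% (−8) |
| 20% | 40% | 60% | 68% (+8) | 48% (−12) |
| 30% | 40% | 60% | 72% (+12) | 42% (−18) |

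If half of those events are still captured, the inflation halves, to 1, 4 and 6 points.

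**3. The same with partial observation.** Let *q* be the 21-day event probability, with constant hazard h = −ln(1 − q)/21, and let a share *f* leave on day *t* for reasons unrelated to risk. The literal share is (1 − f)(1 − q) + f·exp(−h·t). With q = 30%, f = 20%, t = 7, this is 0.8 × 0.7 + 0.2 × 0.888 = 73.8%, against a true 70.0%. Over q = 10–50%, f = 10–30% and t = 0, 7 or 14, the inflation runs from 0.3 to 15 points.

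**4. In counts.** Assume 20 treated patients, 4 with a qualifying event and 4 others not observed for the full window. The literal rule gives 16/20 = 80%, fully observed patients only give 12/16 = 75%, and the worst case gives 12/20 = 60%.

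**5. The scope shift works the other way.** The section's first sentence counts only serious or treatment-related AEs, and its last sentence counts any AE. A patient whose only AE is non-serious and unrelated meets the first rule and fails the second. If a share *a* of patients is in that position, the net change is m·e − a. The two effects cancel at a = 2%, 8% and 12% for the three rows of the table, and a larger *a* makes the net effect downward.

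**The case against.** The section never says that incompletely observed patients are successes. Being without AEs in a window can be read as implying that the window was seen. The word *most* in the follow-up sentence does not show that anyone fell short of three weeks, since the remaining patients may have been followed for longer. No proportion, threshold or test is attached to AE-free status. The secondary outcomes of related AEs and mortality are not limited to completers.

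These points limit what can be claimed. A reader might infer that patients with an AE cannot be completers. The sentence makes being AE-free sufficient for completion, not necessary, so their status is undefined rather than denied. A reader might also expect a completers' table that is AE-free by construction, but no such table is planned. Nor can it be said that the reported share is biased only upward, given the scope shift.

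One remedy that might suggest itself is to score every short window as not met in the main analysis. On the illustrative figures this errs by more than the literal rule does, and in general whenever the event risk is below 50%. It is useful as a bound, not as the main estimate.

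What the objection does not remove is that the only completion and success rule in the documents lacks an observation requirement, and nothing elsewhere supplies one.

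**Conclusion.** The point holds as a defect in the rule, not as evidence that any patient has been misclassified. The wording lets unobserved time be credited as a safety success and leaves completion undefined for patients with an AE. Taken alone, the first effect can only keep or raise the event-free share. The range of about 2 to 12 points rests on assumed loss and event rates, on equal risk in patients who leave, and on all of their events being missed. None of these can be checked from the documents. With the change in AE scope included, neither the size nor the net direction for this trial can be established. The healing-time analysis is not affected. The rule should be corrected before the safety result is reported.

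**What to change.** Replace the last sentence of Study endpoint with two separate rules.

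1. **Completion.** A patient completes the trial if followed to the last planned safety contact or to death, whether or not an AE occurred.
2. **Safety endpoint.** Freedom from serious or treatment-related AEs through three weeks after the last dose, with that AE scope used throughout.

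In the Statistical Analysis Plan, add that rule 2 is estimated in all treated patients by Kaplan-Meier, with event-free patients censored at the last date observed and death counted as an event. State the time origin. Report how many patients had an incompletely observed window. Because censoring may be related to risk (early discharge of patients who are well, transfer of patients who are not), add a worst-case sensitivity analysis that counts those patients as not met.

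The cost is one extra data item (the last date observed), a little more analysis, and a safety figure that may be less favourable. The change can still be applied at the analysis stage if those dates are on record.

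### The only planned analysis, a Kaplan-Meier estimate of healing time, has no rule for patients who die unhealed; censoring them would overstate the proportion healed

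*Combined protocol and SAP*

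**What the plan says.** The Statistical Analysis Plan section reads, in full: "For evaluating the time taken to heal skin erosion, the Kaplan-Meier product-limit estimates method was performed". No other statistical method appears anywhere in the document.

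The Primary Outcome Measures table defines the event as "Definition of complete re-epithelialization as the absence of erosions on the skin", with a time frame of up to 4 weeks. It does not mention death.

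The Detailed Description cites mortality of 30-35% for TEN and 5-15% for SJS and transitional forms, without a time window. Both groups are eligible: "Subject has been diagnosed with Stevens-Johnson syndrome or toxic epidermal necrolysis by at least two dermatologists". Mortality is a separate secondary outcome: "Number of participants with mortality at 30 days, 3 months and 1 year". The design is single-arm, "meaning that there will not be a placebo or control group".

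The Study endpoint section describes completion in terms of adverse events. It gives no censoring rule for healing time and no start of the time scale.

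**The concern.** Censoring assumes that the censored patient would have gone on to heal at the same rate as those still at risk. That can be reasonable for a patient who leaves early, but a patient who has died cannot heal. Kaplan-Meier passes the weight of each censored death to the patients who remain, so the estimated proportion healed rises above the proportion of treated patients who actually healed.

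The plan neither states nor rules out censoring at death. Two analysts could follow it on the same data and report materially different curves.

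With no control group, the absolute healing curve is the primary efficacy result, and no comparison arm shares the bias. If every survivor heals and the last healing follows the last death, the censored curve ends at 100% however many patients died. Mortality counts at three dates show that deaths occurred, but not who died unhealed or when, so a reader cannot correct the curve from them.

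**Working it through.** **Inputs from the documents.** Kaplan-Meier as the only method; a 4-week (28-day) horizon; cited mortality of 5-15% and 30-35%. The documents give no sample size, expected healing rate or SJS/TEN mix, so there is no planned figure to reproduce. The sizes below are illustrations under stated assumptions.

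**Step 1: a case that needs no healing-time model.** Take 20 patients, 3 of whom die unhealed before the last healing, while all 17 survivors heal. With deaths censored, the last patient to heal is alone in the risk set, so the last Kaplan-Meier factor is 1 − 1/1 = 0 and the curve reads 100%. The proportion healed is 17/20 = 85%. With 6 deaths it is 100% against 14/20 = 70%.

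**Step 2: some survivors unhealed at day 28.** Take 20 patients, 2 alive and unhealed at day 28, and *k* unhealed deaths before the first healing. With deaths censored, 1 − KM = (18 − k)/(20 − k). The proportion healed is (18 − k)/20.

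| Deaths k | 1 − KM, deaths censored | Proportion healed |
|---|---|---|
| 1 | 17/19 = 89.5% | 17/20 = 85% |
| 3 | 15/17 = 88.2% | 15/20 = 75% |
| 6 | 12/14 = 85.7% | 12/20 = 60% |

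If the single death comes after the last healing, both figures are 85%. The bias needs an unhealed death followed by a later healing.

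**Step 3: constant hazards.** With healing hazard h and death hazard d, 1 − KM at day 28 is 1 − exp(−28h), and the cumulative incidence of healing is h/(h + d) × [1 − exp(−28(h + d))]. Assume a Kaplan-Meier median of 14 days, so h = ln 2/14 and 1 − KM = 75.0%. Solving for d so that 5, 15, 30 or 35% die unhealed by day 28 gives a cumulative incidence of 72.3, 66.7, 57.8 or 54.7%. The gaps are 2.7, 8.3, 17.2 and 20.3 points. Over assumed medians of 10 to 21 days the gap runs from about 2 to 25 points.

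**Step 4: lognormal healing, simulated.** Assumptions: median healing 16 days, log-SD 0.4, 400,000 patients per setting. In (A) every patient who dies is unhealed. In (B) healing may come before death. For (A) the cumulative incidence can be checked by hand: (1 − m) × Φ(ln(28/16)/0.4) = (1 − m) × 0.919, where m is mortality. With deaths on days 2-20:

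| Mortality | A: 1 − KM | A: cumulative incidence | B: 1 − KM | B: cumulative incidence |
|---|---|---|---|---|
| 2% | 0.918 | 0.900 | 0.92 | 0.906 |
| 5% | 0.917 | 0.873 | 0.92 | 0.885 |
| 15% | 0.912 | 0.781 | 0.92 | 0.819 |
| 30% | 0.902 | 0.642 | 0.92 | 0.718 |
| 35% | 0.899 | 0.598 | 0.92 | 0.683 |

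Range of the day-28 gap over A and B and three death windows (days 2-14, 2-20, 2-28):

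| Share of cited mortality before day 28 | At 5-15% | At 30-35% |
|---|---|---|
| All | 2.4-13.6 points | 14.7-31.6 points |
| Half | 1.2-6.8 | 7.4-15.9 |
| A quarter | 0.6-3.4 | 3.7-8.0 |

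At 2% mortality the gap is 1.0-1.8 points. By case mix (10% mortality in SJS/overlap, 32.5% in TEN, deaths on days 2-20) it is 7-9 points with no TEN, 14-18 with half TEN and 22-28 with all TEN.

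**Step 5: the median.** In a large sample, with all cited mortality before day 28, the censored median is too early by 0.16-1.30 days at 5-15% mortality and 1.14-5.03 days at 30-35%. In simulated 20-patient trials (an assumed size; deaths on days 2-20) it is unchanged in 94-95% of trials at 5% mortality, 55-63% at 15% and 8-17% at 32.5%. At 5% mortality, 36% (A) and 47% (B) of these trials show no gap at all.

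**The case against.** The plan never says that deaths will be censored. Kaplan-Meier with unhealed deaths held at risk to day 28 also fits the sentence and, if nobody else is censored earlier, is unbiased. That stands: the certain fault is a missing rule, and the overstatement follows from one way of filling the gap.

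The primary outcome is a time, and no section names a day-28 proportion. A reader may look only at the median, which hardly moves at SJS-level mortality. That also stands, but a healing curve displays the proportion at every time, and its plateau is where the bias is largest.

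The sizes rest on assumed inputs. The cited mortality has no time window, so placing all of it before day 28 gives the upper range. Exclusions such as "Subject has an active, untreated, or serious infectious disease that is ineffective in treatment, such as sepsis" and severe cardiovascular disease may lower mortality among those enrolled. This stands in full, which is why Step 4 includes the half, quarter and 2% settings.

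Mortality at 30 days nearly matches the 4-week horizon, so deaths are not hidden. This helps, but it does not identify who died unhealed. Finally, this is an uncontrolled pilot in which no test or threshold depends on the estimate. That limits the weight of the point without removing it, because the curve is still the main efficacy result.

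**Conclusion.** The concern holds. The plan has no rule for deaths before healing, its own mortality figures make such deaths foreseeable, and censoring them would overstate healing whenever a later healing follows. The 100% against 85% example shows this without any healing-time model. The percentage-point ranges depend on the assumed healing times, death times and case mix. Large gaps need TEN-level mortality with early unhealed deaths, and there is no gap if nobody dies unhealed. The effect on the median is minor at SJS-level mortality. The plan should be changed on this point, though the defect does not undermine the pilot as a whole.

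**What to change.** Replace the sentence in the Statistical Analysis Plan with:

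> Healing time for the primary outcome is estimated by the cumulative incidence function (Aalen-Johansen), with death before healing as a competing event. Patients alive and unhealed are censored at last assessment or day 28, whichever is first.

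Define day 0, which no section does; the first tofacitinib dose is one option. Report, with 95% confidence intervals, the proportion healed by day 28 and the time by which 50% have healed (not reached, if fewer heal). Add the number of deaths before and after healing.

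Holding unhealed deaths in the Kaplan-Meier risk set through day 28 is simpler, but it gives the same answer only if no one is censored before day 28. With dropout of 10, 20 or 30% (uniform over days 5-28) at 32.5% mortality under A with deaths on days 2-20, it gives 0.614, 0.605 or 0.596, while Aalen-Johansen stays at 0.621. The loss is 0.7 to 2.5 points, so it is a tolerable fallback when dropout is low but not a general substitute.

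The cost is a short text change and a standard software routine. It needs each patient's dates of healing and death, which a time-to-event analysis should already hold but which the documents do not list. The stated study window ended on 2025-07-31, so the change should be dated. If it is made after the data were seen, it should be labelled post hoc and the Kaplan-Meier result shown alongside. The healing figures will look less favourable if patients died unhealed.
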